Emotion processing tasks: Three well-established emotional processing tasks will be assessed in the fMRI scanner: an emotion recognition task, an emotional conflict Stroop task, and an emotional discrimination task. In the emotion recognition task (Gur et al. 2002, Moser et al. 2007, Gur et al. 2010), participants identify positive and negative emotional facial expressions, with identification of the gender of actors as a control task. The primary outcome measures of this task are accuracy, response time, and average BOLD response to positive and negative facial expressions during emotion identification compared to gender identification. In the emotional conflict Stroop task (Etkin et al. 2006, Egner et al. 2008), participants identify the valence of emotional facial expressions (targets) with overlaid emotional words (distractors). Targets and distractors may have congruent or incongruent emotional valence. Primary outcome measures are response time, accuracy, and average BOLD response to incongruent compared to congruent trials, separated by the emotional valence of the distractor. The emotional discrimination task consists of selecting between neutral and negative facial expressions (Hariri et al. 2002, Hariri et al. 2003, Kraehenmann et al. 2015), with selection of geometric figures as a control task. The primary outcome measure is BOLD response in the amygdala to facial affect discrimination compared to the control task (psilocybin was not shown to acutely affect accuracy and response time) (Kraehenmann et al. 2015). Participants will practice these tasks at each preparation meeting (Visits 3 and 4), before the baseline fMRI scan.

Resting-State Scans: Blood-oxygen dependent level (BOLD) data will be collected for 12 minutes during a period of rest. The participant will be asked to simply rest with eyes opened and focused on a single point in the participant's view. This scan will allow us to assess the long-term effects of psilocybin on resting-state brain function, and it will also allow us to assess static and dynamic functional connectivity between brain regions and compare results to numerous other fMRI studies of resting-state brain activity.

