Assessing the effects of psilocybin on emotional processing. We hypothesize that psilocybin administration will lead to impaired recognition of negative emotional facial expressions, decreased emotional conflict to incongruent emotional stimuli during an emotional conflict processing task, decreased negative affect, and increased positive affect one week and one month after psilocybin administration, relative to baseline. Outcome measures of the emotion recognition task and emotional conflict Stroop task will be separately submitted to two-way repeated measures ANOVA, with assessment time-point (baseline, one week and one month post-psilocybin) and emotional valence of stimuli (positive vs negative) as within-subject factors. F-tests will be used to assess whether there is a main effect of assessment time point and an effect of the interaction between assessment time point and emotional valence on each outcome measure. Planned comparisons will be used to test the hypothesis of impaired responding to negative emotional stimuli (confirmed by finding increased reaction time and decreased accuracy), and facilitated responding to positive emotional stimuli (confirmed by finding decreased reaction time and increased accuracy) at each post-psilocybin time point (one week, one month) compared to baseline. Outcome measures of the longitudinal questionnaires will be separately submitted to a one-way repeated measures ANOVA, with assessment time-point as a within-subject factor. An F-test will be used to assess whether there is a main effect of assessment time point on each outcome measure.

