Assessing the effects of psilocybin on the neural circuitry of emotion processing. We hypothesize that psilocybin administration will reduce amygdala BOLD response to negative emotional stimuli during emotion recognition and discrimination tasks, and ACC BOLD response during emotional conflict processing, one week and one month post-psilocybin. Whole-brain BOLD EPI data will undergo standard preprocessing (realignment/motion correction, co-registration across runs, normalization to the MNI template, smoothing, motion censoring or “scrubbing” (Power et al. 2012) , physiological artifact correction (Behzadi et al. 2007) , 36-parameter confound regression and spike regression (Satterthwaite et al. 2013)). Regions of interest (ROI) analysis will be performed, with ACC and amygdala as seed regions, to test the hypothesis of decreased BOLD response to negative stimuli and increased BOLD response to positive stimuli in these regions one week and one month post-psilocybin. The first eigenvector of the signal from all voxels in each region will be submitted to a mixed effects repeated measures ANOVA, with time point and the emotional valence of stimuli as within-subject main effects, and subject as a random effect. Subject-level contrasts will assess effects of task condition at each time point. Second-level t-tests will be used for planned comparisons to test the hypothesis of lower BOLD response to negative stimuli and higher BOLD response to positive stimuli post-psilocybin. We will repeat these analyses as whole-brain voxel-wise analyses to evaluate change outside of hypothesized regions. Preprocessing and whole-brain statistical analysis will be conducted using Statistical Parametric Mapping (SPM; <http://www.fil.ion.ucl.ac.uk/spm/software/spm12/>) in MATLAB. ROI analysis will be conducted using MarsBaR (<http://marsbar.sourceforge.net/>).

Secondary Outcome Questionnaire Measures: Repeated-measures ANOVA will be used when appropriate to assess change between groups and over time within groups in secondary outcome measures. Planned

comparisons will investigate change in questionnaire test scores between pre-session and post-session timepoints.

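### Splitting the Stroop incongruent-versus-congruent contrast by distractor valence mixes conflict with face valence, so valence-specific results can be misread as changes in conflict; the main effect of time is unaffected

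*Combined protocol and SAP*

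**What the plan says.** Study Statistics, Emotion processing tasks, describes the Stroop task as one in which "participants identify the valence of emotional facial expressions (targets) with overlaid emotional words (distractors"). It adds: "Targets and distractors may have congruent or incongruent emotional valence". The trials therefore form a two-by-two set, face valence by word valence. After response time and accuracy, the list of primary outcome measures for the task ends with "average BOLD response to incongruent compared to congruent trials, separated by the emotional valence of the distractor".

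The Statistical plan (effects on emotional processing) submits the Stroop outcomes to a repeated measures ANOVA with "assessment time-point (baseline, one week and one month post-psilocybin) and emotional valence of stimuli (positive vs negative) as within-subject factors". It tests the main effect of time and "an effect of the interaction between assessment time point and emotional valence on each outcome measure". Planned comparisons at each post-dose time look for "impaired responding to negative emotional stimuli (confirmed by finding increased reaction time and decreased accuracy"), and for the reverse with positive stimuli. The same section separately predicts reduced emotional conflict.

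The Statistical plan (neural circuitry) models regional BOLD on time and valence and adds second-level tests for "lower BOLD response to negative stimuli and higher BOLD response to positive stimuli post-psilocybin".

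Neither section says whether valence in the Stroop task means the face or the word, and no model with both factors is specified.

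**The concern.** When the word is held negative, the incongruent trial has to show a positive face and the congruent trial a negative face. When the word is held positive, the faces swap. A score meant to isolate conflict therefore also subtracts one face valence from the other.

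A face difference that stayed constant would drop out of change from baseline. This trial predicts the opposite: responses to negative and positive stimuli are expected to move apart after dosing. If that happens and conflict stays the same, the two split scores move in opposite directions, and one of them can look like the hypothesised reduction in conflict. The Stroop BOLD contrast serves the primary objective, so the meaning of these scores should be settled before analysis.

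**Working it through.** **Inputs.** From the documents: face as target, word as distractor, two valence levels, three time points, 12 participants, and the predicted directions of change. The documents give no Stroop effect size or standard deviation, so every millisecond figure below is an assumption. The only design figure stated, the 75.8% in Power Analysis, concerns connectivity change and is not used here.

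**Algebra.** Write m(face, word) for a trial-type mean, and define

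- conflict C = ½{[m(pos,neg) + m(neg,pos)] − [m(neg,neg) + m(pos,pos)]}, the face-by-word interaction;
- face difference D = ½{[m(pos,neg) + m(pos,pos)] − [m(neg,neg) + m(neg,pos)]}, positive minus negative face.

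Then, exactly and for any set of means:

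- negative-word score = m(pos,neg) − m(neg,neg) = C + D
- positive-word score = m(neg,pos) − m(pos,pos) = C − D
- average of the two = C
- negative-word minus positive-word = 2D

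So a change in D moves the two scores equally and in opposite directions, and leaves their average alone. The time main effect tests change in C. The time-by-valence interaction tests change in D.

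**Illustration, response time.** Assume C = 40 ms throughout and D = 0 at baseline. Negative faces are then slowed by d and positive faces speeded by e, so D becomes −(d + e).

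| d = e (ms) | Negative-word score: 40 − (d + e) | Positive-word score: 40 + (d + e) | Average |
|---|---|---|---|
| 5 | 30 | 50 | 40 |
| 10 | 20 | 60 | 40 |
| 15 | 10 | 70 | 40 |
| 20 | 0 | 80 | 40 |

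**Direction for other outcomes.** If accuracy and BOLD change for faces as predicted for stimuli generally, D rises. The negative-word score then goes up and the positive-word score goes down.

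**How often the tests would be significant.** Simulation of 10,000 trials, n = 12, three time points, conflict fixed at 50 ms, face effects present at both post-dose times, two-sided 5% tests:

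| Face change, negative/positive (ms) | Assumed SD of trial-type means (ms) | Time-by-valence interaction | One-week change, each split score | Time main effect |
|---|---|---|---|---|
| none | 20 or 40 | about 5% | about 5% | about 5% |
| +10/−10 | 40 | 20% | 13% | 5.1% |
| +20/−20 | 40 | 65% | 35% | 5.2% |
| +20/−20 | 20 | 99.9% | 89% | 5.2% |
| +20/+20 | 20 or 40 | about 5% | about 5% | about 5% |

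**Splitting by face instead.** Let W be the positive-minus-negative word difference, averaged over faces. The negative-face score is m(neg,pos) − m(neg,neg) = C + W, and the positive-face score is m(pos,neg) − m(pos,pos) = C − W. If negative words slow responses by 10 ms and positive words speed them by 10 ms, W = −20. An unchanged 40 ms conflict then reads as 20 ms and 60 ms, the same distortion with the word in place of the face.

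**The case against.** Three stronger readings are tempting, and the documents do not support them.

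- A reader might infer that the conflict hypothesis cannot be tested as planned. It can: the planned main effect of time averages the two distractor scores, the face terms cancel, and in the simulation it keeps its nominal level.
- A reader might call the interaction spurious. It is not a false positive. In the scenario above face responding really has changed, as predicted, and the interaction detects that. The risk is attributing it to conflict. Reporting both scores would show them moving in opposite directions, which helps an alert reader.
- A reader might think that splitting by target face cures the problem. It carries the mirror-image confound with word valence, and nothing in the documents shows that word effects are smaller.

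Two further points stand. The phrase about separating by distractor may attach to BOLD alone, and the behavioural comparisons can be read as concerning raw response time and accuracy. For BOLD, the Stroop hypothesis stated first is a lower ACC response during conflict processing, while the amygdala hypothesis names the recognition and discrimination tasks. The later comparison by valence is generic and is not explicitly tied to the Stroop contrast, so a firm claim that the planned BOLD test has the wrong sign would go too far.

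None of this removes the confound from a distractor-specific score, and no section corrects for it.

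**Conclusion.** The concern holds for the valence-split Stroop scores and for what is built on them: comparisons within one distractor valence, and the reading of the time-by-valence interaction as valence-specific conflict. It does not reach the main effect of time. It covers BOLD, and response time and accuracy only if they are split.

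The identity requires only two valence levels, which the plan states. The size depends on assumptions: 10 ms of opposite face change turns an unchanged 40 ms conflict into 20 and 60 ms, and the chance that a one-week split-score change is significant runs from 13% to 89% over the non-zero opposite face effects and SDs tabulated. If both face valences change equally, there is no bias.

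**What to change.** Analyse the Stroop outcomes in a face valence by word valence by time model on the trial-type means:

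- test change in conflict as the face-by-word-by-time term, equivalently the incongruent-minus-congruent score averaged over both valences;
- test the predicted valence effects as face by time;
- estimate word by time separately.

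In both parts of the Statistical plan, state that valence in the Stroop task means the target face in this model. In Study Statistics, say whether response time and accuracy are handled in the same way as BOLD. Do not interpret a distractor-specific score alone as conflict, and do not substitute a split by target face as a confirmatory measure.

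The cost is revised wording in three places, one extra factor in the model and regrouping of the same trials; no new data are needed. The trial also gives up any claim about valence-specific conflict. The split scores could not support that claim, because they do not separate it from a face effect.

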Consent will be obtained at the BPRU at a scheduled meeting after participants have passed telephone screening. Participants will be allowed to take as much time as necessary to decide whether or not to sign consent. Study staff will discuss the consent form with the participant after the participant has read the consent form. Study staff will ask questions to assess the individual's understanding of the consent form. Participants may take the consent form home to review and return to sign consent if they wish. Participants who might be eligible for a future study will be asked to complete IRB-approved HIPAA-IRB Form 3 "Authorization to contact you about future research studies". Participants' files will be kept in a locked room and treated as confidential research material. All data will be collected using the unique identification code numbers assigned to each participant upon entry to the study. No individual identifiable information will be released without written authorization. These procedures have been used in the past to protect confidentiality of study data and no instance of loss of confidential information has occurred.

Participants will be physically and psychologically healthy adult participants (approximately equal numbers of males and females) 18 to 45 years old. Non-English speakers and those with language or hearing impairments will not participate in the study. Participants will be recruited primarily from the Baltimore/Washington DC metro area. Participants will have used hallucinogens in the past, although preference will be given to those who have had minimal prior use (e.g. 1 to 2 prior uses) that was at least 3 months ago. Potential participants will be carefully screened to eliminate those with significant medical or psychiatric illnesses (see below for specific inclusion/exclusion criteria).

We expect to consent up to 100 volunteers at Johns Hopkins (some of whom will not pass the in-person screening), in order to achieve 12 participants who provide complete data.

Screening evaluation will include a history and physical examination, ECG, a 30 cc blood draw for medical screening (e.g., complete blood count and Quest Test 18T Comprehensive metabolic panel with eGFR), a personal and family medical history questionnaire, psychiatric interview (SCID-5), and a urine drug test.

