As per standard BPRU screening procedures, screening physical examination and ECGs will be performed by BPRU medical staff (nurse, mid-level, or physician). ECGs will be interpreted by a cardiologist credentialed and privileged to read ECGs at Bayview Medical Center to determine if a significant abnormality exists. Participants will be requested to refrain from illicit drug use during the course of the study and a urine test will be conducted before the drug session (e.g., various opioids, stimulants and sedatives). Pregnant or nursing women are ineligible; female participants will receive a urine pregnancy test at intake and before the drug session, and must use effective methods of contraception during the study. With regard to psychiatric screening, clinical interviews and a structured psychiatric diagnostic interview (e.g., SCID) will be used to obtain baseline psychological data, including psychiatric history (including family history), psychoactive drug-use history, and information about employment status and current functioning (including mood and psychological and psychosomatic symptoms). Participants will be eligible if they are judged to be psychologically stable and do not meet any of the psychiatric exclusion criteria (as defined by DSM-V). Finally, participants will be required to meet standard inclusion/exclusion guidelines for brain imaging protocols (see below). All inclusion and exclusion criteria are described below:

Inclusion criteria:

- 18 to 45 years old
- Have given written informed consent
- Have at least a high-school level of education or equivalent (e.g. GED), and be fluent in English
- Be healthy and psychologically stable as determined by screening for medical and psychiatric problems via a personal interview, a medical questionnaire, a physical examination, an electrocardiogram (ECG), and routine medical blood and urinalysis laboratory tests
- Agree to consume approximately the same amount of caffeine-containing beverage (e.g., coffee, tea) that he/she consumes on a usual morning, before arriving at the research unit on the morning of the drug session day. If the participant does not routinely consume caffeinated beverages, he/she must agree not to do so on the session day.
- Agree to refrain from using any psychoactive drugs, including alcoholic beverages and nicotine, within 24 hours of each drug administration. The exception is caffeine.
- Agree not to take any PRN medications on the mornings of drug sessions

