Longitudinal Emotion and Social Questionnaires: A battery of questionnaires will be completed one day before, one week after, and one month after psilocybin to assess emotional and social changes. This includes general [the Positive and Negative Affect Scale - X (Watson, Clark 1994) and the Profile of Mood States (McNair, Lorr & Droppleman 1992)] and emotion-specific [the Dispositional Positive Emotions Scale (Shiota, Keltner & John 2006), the Depression Anxiety Stress Scale (Lovibond, Lovibond 1995), and the State Trait Anxiety Inventory (Spielberger et al. 1983)] measures, as well as a measure of social cognition [the Social Value Orientation test (Murphy, Ackermann, & Handgraaf, 2011)]. Outcome measures will consist of the validated scale scores for each questionnaire.

Longitudinal and Follow-Up Questionnaires: Participants will complete the Big Five Inventory (BFI) (John, Naumann & Soto 2008) , the Brief Affective Neuroscience Personality Scales (BANPS) (Barrett, Robins & Janata 2013) , the Tellegen Absorption Scale (Tellegen, Atkinson 1974) , and the Emotion Regulation Questionnaire (Gross, John 2003) which are validated measures of personality traits. These questionnaires will be administered during screening and at the 1-month post-psilocybin imaging session, in order to test the hypothesis that openness and positive emotional personality traits will increase, and negative emotional personality traits will decrease, after psilocybin administration. A prior study in our laboratory found changes in the domain of openness following psilocybin (MacLean, Johnson & Griffiths 2011) .

Statistical plan

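### The personality scales have no score on the day before dosing, so their change to 1 month includes any change between screening and the psilocybin session

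*Combined protocol and SAP*

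**What the plan says.** Secondary objective 2 concerns the effect of psilocybin on personality at 1 week and 1 month. The section Longitudinal and Follow-Up Questionnaires names four instruments for it and fixes their timing: "These questionnaires will be administered during screening and at the 1-month post-psilocybin imaging session". The stated purpose is "in order to test the hypothesis that openness and positive emotional personality traits will increase", with negative emotional traits expected to fall.

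The section just before it, Longitudinal Emotion and Social Questionnaires, treats the other scales differently: "A battery of questionnaires will be completed one day before, one week after, and one month after psilocybin".

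Three other places bear on the point.

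- Emotion processing tasks: "Participants will practice these tasks at each preparation meeting (Visits 3 and 4), before the baseline fMRI scan".
- Inclusion/Exclusion Criteria, on selection: "Participants will be eligible if they are judged to be psychologically stable". Up to 100 people may be consented to obtain 12 with complete data.
- Statistical plan: longitudinal questionnaires go into a one-way repeated measures ANOVA over time point, and secondary questionnaire outcomes get planned comparisons of scores before and after the session.

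The study is open label, with everyone receiving psilocybin and no control arm. The documents give no interval from screening to the session and no adjustment for change before dosing.

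**The concern.** The personality hypothesis is about change after psilocybin, but the only scheduled score before the drug comes from screening. Events between that score and the session fall inside the change that will be tested. The preparation meetings are the clearest example. If preparation, or the rapport built there, moves the scores, that movement is counted as a psilocybin effect.

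A second influence could run the other way. A volunteer being screened might describe himself or herself favourably. Lower negative-trait and higher positive-trait scores at screening would then hide part of the hypothesised change.

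At stake is the interpretation of secondary objective 2. Without a control arm, nothing else in the design shows how much the scores move without the drug, and a missing day-before score cannot be recovered once the data are in.

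**Working it through.** **1. Is there a day-before personality score anywhere?** The opening summary lists questionnaires at screening, 1 day before, 1 week and 1 month, but not by instrument. The two questionnaire sections do go by instrument: the emotion battery has day before, 1 week and 1 month; the personality scales have screening and 1 month. The summary reads as the union of these two schedules, so it does not supply a day-before personality score.

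**2. The plan's own figure.** Power Analysis states 75.8% power for three levels (day before, 1 week, 1 month), 12 subjects and an effect size of 0.25, for connectivity change. Reading 0.25 as Cohen's f in a repeated measures ANOVA (noncentrality f²·n·m/(1−ρ), df 2 and 22), power is 40.9% at ρ = 0.5 and 80.7% at ρ = 0.8; it equals 75.8% at ρ of about 0.776. As ρ is not stated, the figure can be neither confirmed nor refuted. It does not cover a two-point personality comparison, and this point does not depend on it.

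**3. What the planned difference contains.** Write S, D and M for the scores at screening, the day before and 1 month. Then

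M − S = (D − S) + (M − D).

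The first bracket is entirely drug-free. D is not measured, so only the sum is observed and no analysis of S and M can divide it. The ANOVA on two time points tests the same sum.

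**4. Share of time, under assumed intervals.** With w weeks from screening to dosing and 4.3 weeks from dosing to 1 month, the drug-free share of the interval is w/(w + 4.3):

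- w = 2: 2/6.3 = 32%
- w = 4: 4/8.3 = 48%
- w = 8: 8/12.3 = 65%

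The values of w are assumptions. These are shares of calendar time, not of bias.

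**5. What a shift before dosing would do, under assumed values.** Take n = 12, a paired t-test, two-sided 0.05 and no drug effect. A shift of d SD with retest correlation ρ gives a standardised change d/√(2(1−ρ)) and noncentrality √12 times that. For d = 0.2 and ρ = 0.8: 0.2/√0.4 = 0.316. The chance of a significant result is:

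| Shift | ρ = 0.7 | ρ = 0.8 | ρ = 0.9 |
|---|---|---|---|
| 0.1 SD | 7% | 8% | 11% |
| 0.2 SD | 13% | 17% | 29% |
| 0.3 SD | 23% | 32% | 56% |
| 0.5 SD | 53% | 70% | 94% |

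The more stable the scale, the more a given shift matters. Neither the shifts nor the correlations come from the documents.

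**6. Can the drug-free interval serve as a formal control?** The contrast is (M − D) − (D − S) = M − 2D + S. With equal variances σ² and equal correlations ρ, its variance is (1 + 4 + 1)σ²(1−ρ) = 6σ²(1−ρ), against 2σ²(1−ρ) for M − D: three times as large. At n = 12, a standardised change of 0.889 has 80% power as a simple change. In the contrast it becomes 0.889/√3 = 0.513, with power of about 37%.

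**The case against.** The scales are described as validated trait measures, and nothing in the documents suggests that they drift over a few weeks. For a 0.1 SD shift the error rate rises only to between 7% and 11%. Screening can also be a defensible trait baseline, because scores on the eve of a high-dose session may reflect anticipation. And the larger limitation is the uncontrolled design: expectancy, retest and time effects after the session remain whatever baseline is used.

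All of this stands, and it limits the point. It does not remove it. Stability before dosing is an assumption that a repeat baseline would check, and the risk of anticipation is a reason to keep both scores.

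A reader might infer more than the text supports:

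- **That applicants distort their answers before being accepted.** Psychological stability is assessed by clinical and structured diagnostic interview. No section says that the four questionnaires inform eligibility, or that they are completed before acceptance. Favourable self-presentation is possible, but it is neither stated nor quantified.
- **That the interval varies between participants, or that 32% to 65% of the change is drug-free.** The first is not stated; the second mistakes time for bias.
- **That preparation certainly follows the screening score.** This is inferred from the numbering of the meetings as Visits 3 and 4; no visit schedule is shown.

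**Conclusion.** The point holds as a limitation of a secondary objective. The personality change is measured from screening, so it includes any change before the session, and the two planned measurements cannot separate the two parts. This rests on the instrument-level schedule and the single arm.

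The size of the error is unknown. Change from preparation could favour the hypothesis and self-presentation could oppose it, so the result can be called neither inflated nor conservative. The false-positive rates show sensitivity to assumed shifts; they are not estimates for this trial. No stated number is shown to be wrong.

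A separate mismatch needs no assumptions: the objective names 1 week, and the schedule has no personality measurement at 1 week.

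**What to change.** - Keep the screening administration and add the four scales to the existing day-before visit.
- Define the day-before score as the baseline for secondary objective 2. Report the screening-to-1-month change as a sensitivity analysis, in case the day-before score is affected by anticipation.
- Report the screening-to-day-before change with a confidence interval and the length of the interval, as descriptive context.
- Do not adopt a rule that credits psilocybin only when the later change exceeds the earlier one. The intervals may be unequal. With no test or margin, sampling error alone would satisfy such a rule about half the time when the expected changes are equal. The formal contrast has the low power shown above, and a retest effect at the second administration would distort the comparator.
- State that expectancy, retest and time effects after the session remain.
- Reconcile secondary objective 2 with the questionnaire schedule on the 1-week time point.

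The cost is four self-report questionnaires once more for 12 participants at a visit that already takes place, a short addition to the plan, a small extra burden that day and one more repeat of the scales.

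### In the emotion recognition task, lower accuracy and slower responses to negative faces do not by themselves establish impaired recognition, because a shift toward answering 'positive' can give the same pattern

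*Combined protocol and SAP*

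**What the plan says.** Under Study Statistics, Emotion processing tasks, the emotion recognition task is described as one in which "participants identify positive and negative emotional facial expressions, with identification of the gender of actors as a control task". Its outcomes are listed as follows: "The primary outcome measures of this task are accuracy, response time, and average BOLD response to positive and negative facial expressions". The number of response labels and the number of trials are not given.

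Under Statistical plan, in the paragraph on emotional processing, the hypothesis is that "psilocybin administration will lead to impaired recognition of negative emotional facial expressions". Each task outcome goes into a two-way repeated measures ANOVA with time point (baseline, one week, one month) and "emotional valence of stimuli (positive vs negative) as within-subject factors". Planned comparisons of each post-drug time point with baseline then look for "impaired responding to negative emotional stimuli (confirmed by finding increased reaction time and decreased accuracy", and for "facilitated responding to positive emotional stimuli (confirmed by finding decreased reaction time and increased accuracy".

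No section mentions a sensitivity index, a response criterion, false-alarm rates, an unbiased hit rate or a stimulus-by-response table.

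**The concern.** When participants label faces, a wrong answer to one category is an answer that belongs to another. Accuracy on negative faces and accuracy on positive faces are therefore linked through how ready the participant is to give each answer. If that readiness moves toward 'positive', accuracy falls for negative faces and rises for positive faces even though the two are told apart exactly as well as before.

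Such a shift is plausible here. The study is open-label and has no control group, and the same paragraph of the plan predicts "decreased negative affect, and increased positive affect one week and one month after psilocybin administration, relative to baseline". At stake is the conclusion on a secondary objective. The trial could report impaired recognition of negative expressions when its data show only a change in which answer participants favour.

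**Working it through.** The plan gives no figure on this point, so there is nothing to reproduce. The check asks whether a pure response shift can satisfy the plan's rule.

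**Inputs.** From the documents: the two stimulus classes, the outcomes (accuracy and response time), the confirmation rule, and the time-by-valence ANOVA. Assumed, because the documents do not give them: the response format, baseline sensitivity d', the size of the shift s toward 'positive', and all diffusion-model and multi-label parameters.

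**1. Accuracy, two-choice format, equal-variance signal detection.**

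- Accuracy on negative faces = Φ(d'/2 − s)
- Accuracy on positive faces = Φ(d'/2 + s)
- Recovered sensitivity = z(negative accuracy) + z(positive accuracy)

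For d' = 2.0 and s = 0, both accuracies are Φ(1.0) = 84.1%. For s = 0.3, they are Φ(0.7) = 75.8% negative and Φ(1.3) = 90.3% positive. Recovered d' = 0.7 + 1.3 = 2.0, and the criterion moves from 0 to −0.3.

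| Assumed d' | No shift, both valences | s = 0.3: negative | s = 0.3: positive | Recovered d' |
|---|---|---|---|---|
| 1.5 | 77.3% | 67.4% | 85.3% | 1.5 |
| 2.0 | 84.1% | 75.8% | 90.3% | 2.0 |
| 2.5 | 89.4% | 82.9% | 93.9% | 2.5 |
| 3.0 | 93.3% | 88.5% | 96.4% | 3.0 |

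At d' = 2.0, a shift of 0.1 gives 81.6% negative and 86.4% positive; a shift of 0.5 gives 69.1% and 93.3%.

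For contrast, a true loss of sensitivity from 2.0 to 1.6 with no shift lowers both accuracies from Φ(1.0) = 84.1% to Φ(0.8) = 78.8%. In this model, the crossed pattern that the plan predicts is what a shift produces.

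**2. More than two labels.** This is a five-option choice model with strength 3 for the true label and a bias b added to the one positive label.

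- Positive accuracy = e^(3+b) / (e^(3+b) + 4)
- Negative accuracy = e^3 / (e^3 + 3 + e^b)

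For b = 0, both are 83.4%. For b = 0.5, positive accuracy is 89.2% and negative accuracy 81.2%. The direction is the same, but negative accuracy falls by only 2.2 points. The bias scale differs from that in step 1, so the sizes are not directly comparable.

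**3. Reaction time.** This is a simulated diffusion model with boundary 1.6, drift 1.5 in either direction and non-decision time 400 ms. Evidence quality is fixed, and only the starting point moves toward 'positive', from 0.50 to 0.60 of the boundary.

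| | Accuracy | Mean correct RT |
|---|---|---|
| Negative faces | about 92% to 86.9% | 859 to 923 ms |
| Positive faces | about 92% to 95.4% | 859 to 781 ms |

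All four parts of the plan's rule are met with no change in the evidence.

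**4. Built-in safeguards.** The time-by-valence interaction does not separate the explanations, because a shift that lowers one accuracy and raises the other is itself such an interaction. The gender control task does not help either, because no valence answer is given there and a preference among valence answers cannot show.

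**The case against.** Several objections have force.

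- **d' and criterion do not identify the cause of a shift.** If every face simply looks more positive by 0.3 SD and the criterion stays put, the accuracies are again Φ(d'/2 − 0.3) and Φ(d'/2 + 0.3). This stands. A criterion change must not be labelled a mere response preference.
- **A two-choice task yields one d' for both valences.** It cannot carry the valence factor of the planned ANOVA. This stands, so d' has to be added beside accuracy and cannot replace it.
- **The rule pairs accuracy with reaction time.** That is stricter than accuracy alone, but step 3 shows that the pair does not exclude a shift. That result depends on assumed parameters and shows possibility only.
- **The tasks are described as well established, and this is a secondary objective in a 12-person study.** This limits the weight of the point. It does not make the inference valid.

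A reader might also infer more than the documents support:

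- **That a response shift will occur, or is the likeliest explanation.** The documents state the investigators' hypotheses, not what participants expect, and nothing in them ranks the alternatives.
- **That the plan claims better recognition of positive faces.** For positive stimuli it speaks only of facilitated responding. Recognition is named only for negative faces.
- **That the emotional conflict Stroop task needs the same rescoring.** There "participants identify the valence of emotional facial expressions (targets) with overlaid emotional words (distractors", but the hypothesis concerns reduced conflict, not recognition. With the distractor held fixed, one target valence is congruent and the other incongruent, so a d' would merge the two conditions being compared. Averaged over distractor valence, a shift cancels. Assuming d' of 2.5 congruent and 1.5 incongruent, the conflict effect is 89.4 − 77.3 = 12.1 points without a shift. With s = 0.3 it is (82.9 + 93.9)/2 − (67.4 + 85.3)/2, again about 12.1. Within one distractor valence it does not cancel, but d' would not repair that.

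**Conclusion.** The point holds for the emotion recognition task and the negative-face hypothesis. The planned accuracy and reaction-time pattern is compatible with unchanged discrimination, so it cannot by itself support a conclusion of impaired recognition. The accuracy crossover appears in every two-choice case computed and in the five-option model. Its size rests on assumptions: for a 0.3 SD shift in a two-choice task, negative accuracy falls by 8.3 points at d' = 2.0 (84.1 − 75.8), by 9.9 at d' = 1.5 (77.3 − 67.4) and by 4.8 at d' = 3.0 (93.3 − 88.5). It may be smaller with more labels. The finding is that the rule cannot separate two explanations, not that the unwanted one is true. The primary fMRI objective is not affected.

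**What to change.** In Emotion processing tasks and in the Statistical plan, for the emotion recognition task only:

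1. Keep accuracy and reaction time in the planned time-by-valence ANOVA.
2. State the response format. From the stimulus-by-response table at each visit, add d' and criterion if there are two choices, or unbiased hit rates by emotion if there are more than two labels. Compare each with baseline.
3. Conclude that recognition of negative expressions is impaired only if d', or the negative-emotion unbiased hit rate, falls.
4. If only the criterion moves, report a valence-related shift in responding, and state that d' and criterion cannot tell a response preference from faces looking more positive.
5. Leave the Stroop conflict contrast as planned.

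The cost is rescoring of recorded responses, provided that individual responses are stored, and a few sentences in the plan. There are four drawbacks. Cells at 0% or 100% need a standard correction. A two-choice task gives no separate d' for each valence. The conclusion is more limited if only the criterion moves. The unbiased hit rate reduces the problem but does not remove it. In the five-option example with equal trials per label, it is hit rate squared divided by total use of the label. For a negative label this goes from 0.834²/1.000 = 69.5% to 0.812²/(0.812 + 3 × 0.0404 + 0.0269) = 68.7%. That is a fall of about 0.9 points before rounding, against 2.2 for raw accuracy, so a very small fall should be read with care.
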